5.1.4 Inclusion of Women and Minorities

Both men and women of all races and ethnic groups are eligible for this trial

5.2 Registration Procedures

5.2.1 General Guidelines

Each patient must sign and date an informed consent form before undergoing any study specific procedure unless a procedure is being performed as part of the patient's standard of care.

Enrollment in the study requires that all inclusion and exclusion criteria have been met. Enrolment occurs upon confirmation of registration from the NYULMC PCC Clinical Trials Office. The following materials must be submitted to the Research Coordinator for registration:

1. Complete signed and dated informed consent form
2. Complete signed and dated eligibility checklist
3. All supporting documentation verifying each criterion has been met

Registration will occur within 48 hours of research coordinator receipt of all of the above documents. A written confirmation of enrollment including a unique study identification number assigned by the research coordinator will be distinguished to the study team upon registration.

Once eligibility is verified, a unique patient study number will be issued within 24 hours of receiving all required registration material. The patient will not be identified by name. This is the point, at which, the patient is considered accrued on study.

5.2.2 Multi-Site Surveillance

As the lead investigator in a multi-site trial, the Principal Investigator is responsible for organizing and conducting monthly teleconferences with all participating sites. Each participating site will be responsible for submitting the results and recommendations from the DSMC's quarterly reviews to their IRB of record at the time of continuing review. Additionally, the NYU Langone Health PCC Clinical Trial Office, Quality Assurance Unit will provide a remote extensive monitoring including real-time review of all eCRFs to ensure

completeness and compliance with the protocol (100% source documentation verification). Additionally, a first subject audit is to be completed within four weeks of enrollment. Decisions from the DSMB will be disseminated to other study sites during routine calls of the investigators at each site, which will occur monthly.

5.2.3 Patient Registrations at Other Participating Institutions

Enrollment at addition sites can begin once each site's IRB has approved this protocol, a copy of each site's IRB approval, Citi training certificates, Medical Licenses and signed CVs are provided to NYU Langone Health Perlmutter Cancer Center (PCC) Clinical Trials Office. Once, all required documents are provided to NYU Clinical Trials Office and an SIV is conducted, an activation notification will be sent to the PI and research coordinator of that site. Central registration for this study will take place at NYU Langone Health PCC Quality Assurance Unit ([contact]).

Each patient must sign and date an informed consent form before undergoing any study specific procedures unless a procedure is being performed as part of the patient's standard of care. Once a patient has signed consent, each site must notify the NYU Langone Health PCC Quality Assurance Unit and forward a copy of the signed consent to NYU Langone Health PCC Clinical Trials Office within 24 hours.

Enrollment in the study requires that all inclusion and exclusion criteria have been met. Enrollment occurs upon confirmation of registration from the NYU Langone Health PCC Clinical Trials Office. The following materials must be submitted to the Quality Assurance Unit at NYU Langone Health via email ([contact]):

1. Complete signed and dated informed consent form
2. Complete signed and dated informed consent checklist
3. Complete signed and dated eligibility checklist
4. All supporting documentation verifying each criterion has been met.

Registration will occur once the Senior Research Nurse for Quality Assurance conducts a central review of the submitted materials. Once eligibility is verified, a unique subject study number will be issued within 48 hours of receiving all required registration material. This number is unique to the participant and must be written on all data and correspondence for the participant. The NYU Langone Health PCC CTO will return a signed eligibility confirmation worksheet email with the subject's unique study number.

The subject will not be identified by name. This is the point, at which, the patient is considered accrued on study. Protocol treatment should begin within the designated timeframe; issues that would cause treatment delays should be discussed with the overall PI, [name]. Subjects must not start any protocol procedures prior to

registration; each participating institution will order the study agent directly from the supplier.

Each site is responsible for reporting all unexpected problems involving risks to participants or others to NYU Langone PCC Clinical Trials Office and to their IRB as per site institutional policy.

Please email all SAEs to [contact], assigned medical monitor, and [name].

5.2.4 Process of Consent

Consent will be obtained by a participating investigator, or allied health professional/research coordinator/research nurse, all of whom have completed requisite training for human subject research and have been instructed by the Principal Investigator about the research study and consent process. Investigators will review the informed consent form with patients and address any questions or concerns prior to obtaining written informed consent for participation and HIPAA authorization.

Patients who are evaluated and/or treated by physicians in the oncology program will be given a consent form (attached) describing participation in the study. Patients will be given adequate time to read the consent form. After patients have been evaluated by their physician, they will be given time to ask questions about the study in private exam rooms. Questions will be answered by a participating physician, physician's assistant, nurse, or research coordinator, all of whom have completed requisite training for human subject research. Investigators will review the informed consent form with patients and address any questions or concerns prior to obtaining written informed consent for participation. Investigators will stress that participation in the study is completely voluntary and will not affect the care patients receive or result in any loss of benefits to which patients are otherwise entitled.

For non-English speaking patients, institutional translation services will be utilized. All procedures for consenting non-English speaking patients will be in accordance with NYULMC PCC CTO guidelines and policy.

For patients who cannot read. A witness, not related to the research study will be present. The consent will be read to the patient. The patient will also be allowed to ask any questions s/he may have. The investigator will ask the patient questions to ensure s/he understands the study. If the investigator determines the subject understands the study, the patient will mark an X where his/her name would go and the witness will sign the consent form.

5.2.5 Documentation of Consent

The Principal Investigator will be responsible for documentation in the medical record that consent has been obtained from all participants. A signed copy of the consent form will be given to each participant. Original consent forms will be stored in the subject's medical chart.

5.3 Trial Treatments

The treatment to be used in this trial is outlined below in Table 6

Table 6: Trial Treatment

Drug	Dose/Potency	Dose Frequency	Route of Administration	Regimen/Treatment Period	Use
Lenvatinib	20mg	QD	PO	Lead in as single agent day 1-7, then to continue daily on Q3 week schedule	Experimental
Pembrolizumab	200 mg	Q3W	IV infusion	Day 1 of each 3 week cycle, starting following 7 day lead in with lenvatinib (Day 8 of study)	Experimental

Trial treatment should begin on the day of randomization or as close as possible to the date on which treatment is allocated/assigned.

5.3.1 Dose Selection and Modification

5.3.1.1 Dose Selection

Dose and schedule are based on phase I results from ongoing study "Phase 1b/2 Trial of Lenvatinib Plus Pembrolizumab in Subjects With Selected Solid Tumors" NCT02501096. Subjects with non-small cell lung cancer, renal cell carcinoma, endometrial cancer, urothelial cancer, squamous cell carcinoma of the head and neck, or melanoma were treated with pembrolizumab 200mg IV every three weeks with escalating doses of lenvatinib in order to determine the maximum tolerated dose. The MTD was determined to be 20mg of lenvatinib daily in combination with pembrolizumab.

5.3.1.2 Dose Modification (Escalation/Titration/Other)

If one therapeutic agent is either held or permanently discontinued secondary to toxicity, then therapy with the other study agent should continue and the subject should remain on-study with full adherence to all protocol-related requirements.

5.3.1.3 Dose Interruptions and Modifications for Pembrolizumab

Adverse events (both non-serious and serious) associated with pembrolizumab exposure may represent an immunologic etiology. These adverse events may occur shortly after the first dose or several months after the last dose of treatment. Pembrolizumab must be withheld for drug-related toxicities and severe or life-threatening AEs as per 3 below. See Section 5.5.1 for supportive care guidelines, including use of corticosteroids.

Table 7: Dose Modification Guidelines for Pembrolizumab Adverse Events (AEs)

Toxicity	Hold Treatment For Grade	Timing for Restarting Treatment	Treatment Discontinuation
Diarrhea/Colitis	2-3	Toxicity resolves to Grade 0-1	Toxicity does not resolve within 12 weeks of last dose or inability to reduce corticosteroid to 10 mg or less of prednisone or equivalent per day within 12 weeks
	4	Permanently discontinue	Permanently discontinue
AST, ALT, or Increased Bilirubin	2	Toxicity resolves to Grade 0-1	Toxicity does not resolve within 12 weeks of last dose
	3-4	Permanently discontinue (see exception below) ^a	Permanently discontinue
Type 1 diabetes mellitus (if new onset) or Hyperglycemia	T1DM or 3-4	Hold pembrolizumab for new onset Type 1 diabetes mellitus or Grade 3-4 hyperglycemia associated with evidence of beta cell failure	Resume pembrolizumab when patients are clinically and metabolically stable
Hypophysitis	2-4	Toxicity resolves to Grade 0-1. Therapy with pembrolizumab can be continued while endocrine replacement therapy is instituted	Toxicity does not resolve within 12 weeks of last dose or inability to reduce corticosteroid to 10 mg or less of prednisone or equivalent per day within 12 weeks
Hyperthyroidism	3	Toxicity resolves to Grade 0-1	Toxicity does not resolve within 12 weeks of last dose or inability to reduce corticosteroid to 10 mg or less of prednisone or equivalent per day within 12 weeks
	4	Permanently discontinue	Permanently discontinue
Hypothyroidism		Therapy with pembrolizumab can be continued while thyroid replacement therapy is instituted	Therapy with pembrolizumab can be continued while thyroid replacement therapy is instituted
Infusion Reaction	2 ^b	Toxicity resolves to Grade 0-1	Permanently discontinue if toxicity develops despite adequate premedication
	3-4	Permanently discontinue	Permanently discontinue
Pneumonitis	2	Toxicity resolves to Grade 0-1	Toxicity does not resolve within 12 weeks of last dose or inability to reduce corticosteroid to 10 mg or less of prednisone or equivalent per day within 12 weeks Or 2 nd episode
	3-4	Permanently discontinue	Permanently discontinue
Renal Failure or Nephritis	2	Toxicity resolves to Grade 0-1	Toxicity does not resolve within 12 weeks of last dose or inability to reduce corticosteroid to 10 mg or less of prednisone or equivalent per day within 12 weeks
	3-4	Permanently discontinue	Permanently discontinue

Toxicity	Hold Treatment For Grade	Timing for Restarting Treatment	Treatment Discontinuation
All Other Drug-Related Toxicity ^c	3 or Severe	Toxicity resolves to Grade 0-1	Toxicity does not resolve within 12 weeks of last dose or inability to reduce corticosteroid to 10 mg or less of prednisone or equivalent per day within 12 weeks
	4	Permanently discontinue	Permanently discontinue

Note: Permanently discontinue for any severe or Grade 3 drug-related AE that recurs or any life-threatening event.

^a For patients with liver metastasis who begin treatment with Grade 2 AST or ALT, if AST or ALT increases by greater than or equal to 50% relative to baseline and lasts for at least 1 week then patients should be discontinued.

^b If symptoms resolve within one hour of stopping drug infusion, the infusion may be restarted at 50% of the original infusion rate (e.g., from 100 mL/hr to 50 mL/hr). Otherwise dosing will be held until symptoms resolve and the subject should be premedicated for the next scheduled dose.

^c Patients with intolerable or persistent Grade 2 drug-related AE may hold study medication at physician discretion. Permanently discontinue study drug for persistent Grade 2 adverse reactions for which treatment with study drug has been held, that do not recover to Grade 0-1 within 12 weeks of the last dose.

Dosing interruptions are permitted in the case of medical / surgical events or logistical reasons not related to study therapy (e.g., elective surgery, unrelated medical events, subject vacation, and/or holidays). Subjects should be placed back on study therapy within 3 weeks of the scheduled interruption, unless otherwise discussed with the Sponsor (NYU Langone Medical Center). The reason for interruption should be documented in the subject's study record.

5.3.1.4 Dose Interruptions and Modifications for Lenvatinib

5.3.1.4.1 Management of Hypertension

Hypertension is a recognized side-effect of treatment with drugs inhibiting VEGF signaling. Investigators should therefore ensure that subjects enrolled to receive treatment with lenvatinib have BP < 140/90 mmHg at the time of study entry and, if known to be hypertensive, are on antihypertensive therapy before they start treatment with lenvatinib. The early detection and effective management of hypertension are important to minimize the need for lenvatinib dose interruptions and reductions. Antihypertensive agents should be started as soon as the BP is confirmed to be > 140/90 mmHg on 2 assessments 1 hour apart. The choice of antihypertensive treatment should be individualized to the subject's clinical circumstances and follow standard medical practice. For previously normotensive subjects, monotherapy with one of the classes of antihypertensives should be started when BP > 140/90 mmHg is first observed on 2 assessments 1 hour apart. For those subjects already on antihypertensive medication, the dose of the current agent may be increased, if appropriate, or one or more agents of a different class of antihypertensive should be added. For subjects with hypertension and proteinuria, treatment with an angiotensin-converting enzyme inhibitor or angiotensin-II receptor antagonist is preferred.

Lenvatinib should be withheld in any instances where a subject is at imminent risk to develop a hypertensive crisis or has significant risk factors for severe complications of uncontrolled hypertension (e.g., BP > 160/100 mmHg, significant risk factors for cardiac disease, intracerebral hemorrhage, or other significant co-morbidities). Once the blood pressure is controlled, lenvatinib should be resumed as described below.

The following guidelines should be followed for the management of systolic BP > 160 mmHg or diastolic BP > 100 mmHg confirmed on repeat measurements after an hour:

- Continue study drug and institute antihypertensive therapy for subjects not already receiving this.
- For those subjects already on antihypertensive medication, the dose of the current agent may be increased, if appropriate, or one or more agents of a different class of antihypertensive should be added.
- If systolic BP > 160 mmHg or diastolic BP > 100 mmHg persists despite maximal antihypertensive therapy, then lenvatinib administration should be interrupted and restarted at a dose of 14 mg once daily when BP < 150/95 mmHg.
- If systolic BP > 160 mmHg or diastolic BP > 100 mmHg recurs on the 14 mg once daily dose despite optimal management of hypertension with antihypertensive medications (either by dose increase or the addition of a different class of antihypertensive), then lenvatinib administration should be interrupted and restarted at a dose of 10 mg once daily when BP < 150/95 mmHg.
- If systolic BP > 160 mmHg or diastolic BP > 100 mmHg recurs on the 10mg once daily dose despite optimal management of hypertension with antihypertensive medications (either by dose increase or the addition of a different class of antihypertensive), then study drug administration should be interrupted and additional dose reduction should be discussed with the sponsor.

The following guidelines should be followed for the management of Grade 4 hypertension (life threatening consequences):

- Institute appropriate medical management.
- Discontinue lenvatinib

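### Section 5.3.1.4.1 says both to withhold and to continue lenvatinib at a blood pressure above 160/100 mmHg, and leaves the restart threshold and dose after an early hold to interpretation

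*Combined protocol and SAP*

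**What the plan says.** **Lenvatinib, Section 5.3.1.4.1.** The withhold sentence reads "Lenvatinib should be withheld in any instances where a subject is at imminent risk to develop a hypertensive crisis or has significant risk factors" and continues to severe "complications of uncontrolled hypertension (e.g., BP > 160/100 mmHg, significant risk factors for cardiac disease, intracerebral hemorrhage". It is followed by "Once the blood pressure is controlled, lenvatinib should be resumed as described below".

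The next paragraph gives guidelines for "management of systolic BP > 160 mmHg or diastolic BP > 100 mmHg confirmed on repeat measurements after an hour". Its first bullet is "Continue study drug and institute antihypertensive therapy for subjects not already receiving this". Its second tells sites to raise or add antihypertensives in subjects already on them. Interruption comes later. If the pressure "persists despite maximal antihypertensive therapy, then lenvatinib administration should be interrupted and restarted", the drug is to be "restarted at a dose of 14 mg once daily when BP < 150/95 mmHg". If it "recurs on the 14 mg once daily dose despite optimal management of hypertension with antihypertensive medications", the drug is interrupted again and restarted at 10 mg at the same threshold. If it returns on 10 mg, the drug is interrupted and any further reduction goes to the sponsor for discussion.

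**Table 8** has general interruption and dose rules by grade. Its title covers lenvatinib-related adverse events, but it sits in Section 5.3.1.4.2 on proteinuria, and the text there points only proteinuria to it.

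**Pembrolizumab.** Table 7 (Section 5.3.1.3) and Table 9 (Section 5.5.1, immune-related events) both give dosing actions for hyperthyroidism and hypophysitis.

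**The concern.** These are dosing instructions for a known safety problem in a multi-site trial. Section 4.1.4.6 puts hypertension first among the common lenvatinib reactions and names it the leading cause of dose reduction. If the text supports two opposite actions at one blood pressure, two sites can each follow the protocol as written, one holding the drug and one continuing it. They can then bring subjects back at different pressures and doses. A monitor could not call either a deviation. The monthly cross-site calls (Section 5.2.2) and the sponsor discussion of delays over 28 days (Table 8, note a) may narrow such differences, but both come after the dosing decision.

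**Working it through.** No figure in the plan bears on this point, so the check sets the instructions side by side.

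**Step 1. Do the triggers overlap?**

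| Instruction in 5.3.1.4.1 | Trigger | Action | Restart |
|---|---|---|---|
| A, withhold sentence | Crisis risk or significant risk factors; BP > 160/100 is a listed example | Withhold | When controlled, by the rules below |
| B1, first bullet | Systolic > 160 or diastolic > 100, confirmed after an hour | Continue and start antihypertensives | Not applicable |
| B3, third bullet | Same BP after maximal treatment | Interrupt | 14 mg at < 150/95 |
| B4, fourth bullet | Same BP again on 14 mg despite optimal management | Interrupt | 10 mg at < 150/95 |
| B5, fifth bullet | Same BP again on 10 mg despite optimal management | Interrupt | Sponsor discussion |

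Take a subject on the 20 mg dose of Table 6, with no antihypertensive and a confirmed 170/105 mmHg. Since 170 > 160 and 105 > 100, the reading fits the example in A, so withhold. It is confirmed, so it also fits B1, so continue.

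**Step 2. Does any wording separate A from B1?** Limiting A to high-risk subjects does not, because the pressure is itself an example of what puts a subject in A. Confirmation does not either. A does not ask for it, and if confirmation were the dividing line, an unconfirmed reading would be held while a confirmed one was treated through. No exception clause links the two paragraphs.

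**Step 3. Follow the restart pointer.** Suppose the same subject is held under A.
- B3 requires maximal treatment to have failed. None has been started.
- B4 and B5 require a reduced dose. The subject is on 20 mg.

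No restart bullet has its condition met. A site may borrow 150/95 mmHg from B3. It may also find that Section 5.1.2, criterion 9, defines adequate control as below 140/90 mmHg, but that is a screening criterion. For dose, it may return to 20 mg or borrow 14 mg from B3. The text does not choose.

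**Step 4. Does Table 8 settle it?** Its title would allow it to apply to hypertension, but its placement and introduction do not say so. The documents also assign no grade to a BP above 160/100 mmHg. It therefore raises a question of scope and gives no answer.

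**Step 5. Tables 7 and 9 (secondary).**

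| Event | Table 7 | Table 9 |
|---|---|---|
| Hyperthyroidism, Grade 4 | Permanent discontinuation | Withhold or permanently discontinue, at the investigator's or treating physician's discretion |
| Hypophysitis, restart after Grade 3-4 | Grade 0-1, followed by wording that therapy can continue during endocrine replacement | Note allows resumption at Grade 2 or below if controlled on hormonal replacement |

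Section 5.3.1.3 uses mandatory language. Section 5.5.1 calls its measures suggestions and refers back to 5.3.1.3 for dose modification. Yet Table 9 is titled as dose modification and has its own action column. No order of precedence is stated.

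**Step 6. Size.** Section 4.1.4.6 gives, for lenvatinib, hypertension in at least 30%, dose reduction for it in 13%, serious hypertension in 3% and discontinuation for it in 1%. Section 4.2.2.2 reports Grade 3 hypertension in one of ten patients on the combination at 20 mg. These show relevance, but none is a rate of BP above 160/100 mmHg. What can be counted is the instructions: two opposite actions for one pressure.

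**The case against.** The best defence is that the withhold sentence is aimed at subjects in danger: its operative condition is imminent crisis or significant risk factors, and the next paragraph handles everyone else. That is probably close to the intention, but the sentence lists the pressure itself as an example, so the overlap stays.

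Several stronger readings are tempting, and the documents do not support them.
- **That an early hold has no link to any restart rule.** There is a link, and 150/95 mmHg is the only restart pressure below it. The gap is narrower: control is not defined there, and the rules reached carry conditions that an early hold does not meet.
- **That there are three rival restart criteria, or a conflict over an 8 mg step.** Both need Table 8 to apply to hypertension and the event to be Grade 3, and the documents establish neither. Sponsor discussion after 10 mg does not exclude 8 mg. The 14 mg and 10 mg steps and the Grade 4 action agree in both places.
- **That Tables 7 and 9 flatly contradict each other.** On Grade 4 hyperthyroidism Table 9 is looser rather than opposite: following Table 7 breaches nothing in it. The hypophysitis difference depends on an ambiguous cell in Table 7; read as a separate permission to continue, it shrinks or disappears. The cross-references lean towards Table 7, though the one in 5.5.1 sits in a note about unrelated events and is not conclusive.
- **That the response endpoint is affected.** Section 8.1 requires both agents for at least 2 cycles in its main route to evaluability, so inconsistent holds could in principle matter. The documents give no means of sizing this, and it is not claimed.

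**Conclusion.** The withhold and continue instructions conflict as written for a confirmed pressure above 160/100 mmHg. This rests on the text alone. The restart point holds as an ambiguity: threshold and dose after an early hold are open to interpretation. Whether Table 8 reaches hypertension is unstated.

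The pembrolizumab differences are real but of lower severity. Their frequency is also uncertain: Section 4.1.2.6 gives hyperthyroidism of any grade at 2.2% in two monotherapy studies, and drug-related serious hyperthyroidism and hypophysitis at 0.3% each. Neither figure is a Grade 4 rate.

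No count of affected subjects can be derived. The matter is one of safety and clarity and should be fixed. No view is taken on which clinical rule is right.

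**What to change.** The sponsor must reconcile the paragraphs of Section 5.3.1.4.1 so that a BP above 160/100 mmHg has one stated action, and any hold, whenever made, has one stated restart criterion and dose step. The section must also say whether Table 8 applies to hypertension.

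Separately, and with lower priority, the sponsor must reconcile Table 7 and its notes with Table 9 and its notes for hyperthyroidism and hypophysitis, and state which table controls pembrolizumab dosing.

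The cost is a protocol amendment submitted to the IRB (Section 10.3) and a memo to sites. Sample size, decision rules and data collection do not change.
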